5.3.1.4 Sensitivity Analysis

For subjects who had clinical significant increased doses or new introduction of ACE inhibitors/ARB post baseline, a sensitivity analysis will be performed where data is imputed after the point of ACE inhibitors/ARB treatment change. The last observation prior to the start of concomitant medication will be carried forward to subsequent time points. Note that LOCF can only be applied within a treatment period and not across periods. Sensitivity analysis will be carried

out similar to the primary and secondary analyses of UPCR as described in Sections 5.3.1.1 and 5.3.1.2:

- Percent change from baseline to Week 26 during the double-blind treatment period (separately for elevated C5b-9 stratum and combined C5b-9 strata)
- Percent change from Week 26 to Week 52 during the Avacopan treatment period (separately for elevated C5b-9 stratum and combined C5b-9 strata)
- Percent change from baseline across the entire study with comparison between treatments at Week 52 period (separately for elevated C5b-9 stratum and combined C5b-9 strata)

Additional sensitivity analysis of UPCR may be conducted to explore other aspects of changes of ACE inhibitor/ARB treatments for C3G, such as clinical significant dose decreases in Period A.

5.3.2 Change and Percent change from baseline in eGFR during the 26 Week placebocontrolled treatment period

The same analysis as described for UPCR will be carried out for estimated glomerular filtration rate (eGFR) including primary and secondary analyses. eGFR will not be log_e-transformed before entering into the MMRM analysis. eGFR is computed at Baseline, Weeks 2, 4, 12, 20, 26 during the 26 week double-blind treatment period and Weeks 32, 38, 52 and 60 during the active treatment and follow-up period.

A subgroup analysis for the change and percent change from baseline in eGFR will be performed in patients with impaired renal function at baseline eGFR ($<60, \ge 60 \text{ mL/min/1.73 m}^2$), if there are sufficient number of subjects in these subgroups

5.3.3 Change from baseline in the C3G Histological Index for disease chronicity during the 26 Week placebo-controlled treatment period

C3G Histologic Index for disease chronicity considers 4 lesions and can assume a score from 0 to 10. See Section 2.3.4 for further details on the calculation of C3G Histologic Index for disease chronicity.

The analysis of C3G Histologic Index for disease chronicity will be carried as described in Section 5.2 for C3G Histologic Index for disease activity including all secondary, completer and sensitivity analyses.

Similar to Histological Index for Disease Activity, the primary analysis will be carried out by imputing missing data for the 4 lesions that comprise the Histological Index for Disease Chronicity. The multiple imputation model will include the two stratification factors (disease type [C3G or DDD] and kidney transplant status [Y/N]), treatment group, in addition to values at each visit from baseline through week 26. Glomerulosclerosis is calculated from % glomeruli with global and %glomeruli with segmental sclerosis which is then summed to calculate total percent of glomeruli involved. If individual values are missing, the total percent of glomeruli will be imputed.

For each lesion component, 100 'complete' datasets will be generated using SAS[®] PROC MI. The seeds for the imputation will be specified as '16222', '71217', '60993', and '19457', for imputation of 4 lesion chronicity scores, respectively. Imputed individual lesion component scores will then be classified into scale scores (e.g., Interstitial fibrosis = 18% would translate to a scale score of 1). The 'complete' datasets for the individual components of the lesion chronicity scores will be merged by imputation number and summed to calculate the Histological Index for Disease Chronicity and creation of 100 'complete' datasets for evaluation of chronicity scores.

For the subjects with missing data, continuous results of glomerulosclerosis and cortical tubulointerstitial area involved will be imputed first and then their categorical results will be calculated in order to calculate Histological Index for Disease Chronicity.

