5.9. Concomitant Medications and Restrictions

In order not to disrupt patient care, the protocol will allow initial continuation of treatment with glucocorticoids, immunosuppressants, calcineurin inhibitors, or RAAS inhibitors at the start of the study, at the same or lower dose than what was given prior to the study. Treatment with these other drugs may be reduced or stopped during the study if, in the opinion of the treating physician, the patient's condition justifies it. Adjustments of tacrolimus and cyclosporine doses to ensure these medications are at goal trough levels for maintenance of immunosuppression in transplant patients will be allowed during the study.

With the exception of RAAS inhibitors, dose increases of these concomitant treatments, or introduction of new treatments for C3G, will not be allowed during the study period (active treatment period) unless the patient's condition deteriorates to the extent that the Investigator deems it in the best interest of the patient to do so. This will be considered a treatment failure.

Eculizumab (and other anti-C5 antibodies) and investigational drugs will not be allowed during the study. The rationale for excluding anti-C5 antibodies is that these drugs act on the same branch of the complement pathway (C5), even though avacopan is selective for the C5aR. Therefore, eculizumab may interfere with the safety and efficacy assessment of avacopan. Investigational drugs have unknown effects and will therefore be excluded from the study.

Plasma exchange or infusion during the study will also not be allowed, since these may interfere with the efficacy and safety evaluation of avacopan.

Drugs that are strong inducers of the CYP3A4 enzyme, such as carbamazepine, phenobarbital, and phenytoin, rifampin, or St. John's wort are prohibited during the study because these drugs may substantially reduce the plasma concentrations of avacopan and reduce its effectiveness. If a patient requires one of these drugs, the Medical Monitor needs to be contacted to discuss the situation.

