5.3 Secondary Efficacy Analyses

5.3.1 Percent change from baseline in UPCR during the 26 Week placebo-controlled treatment period

Urinary protein:creatinine ratio (UPCR) is computed at Baseline, Weeks 1, 2, 4, 12, 20, 26 during the 26 week double-blind treatment period and Weeks 28, 32, 38, 52 and 60 during the active treatment and follow-up periods.

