5.3.1.1 Primary Analysis

The primary analysis will be based on the ITT population in the elevated C5b-9 stratum (>244 ng/ml). The primary analysis of percent change from baseline (in the form of ratio) in UPCR over 26 weeks will be performed in the subjects in ITT population whose UPCR is abnormal at baseline using a mixed effect model for repeated measures (MMRM) analysis with treatment group, visit, treatment-by-visit interaction and baseline as a covariate. The abnormal UPCR value is defined as UPCR ≥ 0.15 g/g. Subjects will be considered as repeated measure units over visits. Point estimates and corresponding 95% confidence intervals will be estimated for the difference between avacopan and placebo across 26 weeks using a simple contrast from the model.

To alleviate the skewness of the data, UPCR will be log_e-transformed before entering into the MMRM analysis. Least squares mean differences between avacopan and the placebo group in the percent change from baseline to Week 26 log(UPCR) will be back transformed to obtain the estimate for the baseline-adjusted reduction from control in UPCR. Corresponding P-values will also be presented.

In the MMRM model, missing data will not be imputed. Toeplitz covariance matrix will be used to model within-subject variance-covariance structure for the model errors. If the model does not converge using the Toeplitz covariance matrix, AR(1) covariance matrix will be used. If convergence is still not met, then compound symmetry (CS) will be used.

The code used to generate the MMRM analysis will be similar to the following:

```
Note:
TRT01AN = randomized treatment group (numeric): 1=Placebo, 2=Avacopan
VISITN = Visit Number
LR2BASE = Ratio of Visit Value to Baseline Value (log-transformed)
LBASE = Baseline value of response (log transformed)
proc mixed data=lablog;
class SUBJID VISITN TRT01AN(ref='1');
model LR2BASE = TRT01AN VISITN TRT01AN*VISITN LBASE/
solution cl ddfm=kr;
Repeated VISITN / TYPE=TOEP sub=SUBJID;
**use AR(1) if no convergence, then CS;
lsmeans VISITN*TRT01AN / alpha=0.05 cl pdiff slice=VISITN;
ods output LSMeans=LSM
```

5.3.1.2 Secondary Analysis

run;

The same analysis as described for the primary analysis will also be performed for the following:

- Percent change from baseline over 26 weeks during the double-blind treatment period in the combined C5b-9 strata (subjects with elevated C5b-9 blood levels and non-elevated C5b-9 blood levels)

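### SAP 5.3.1.4 carries UPCR forward after an ACE inhibitor/ARB start or increase, which attenuates a treatment effect that is still building and can bias the contrast if use differs between arms

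*SAP*

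**What the plan says.** Protocol 5.9 treats RAAS inhibitors differently from other background treatment: "With the exception of RAAS inhibitors, dose increases of these concomitant treatments, or introduction of new treatments for C3G, will not be allowed" unless the patient deteriorates, and such a change then counts as treatment failure. ACE inhibitor/ARB starts and increases can therefore occur in either arm without making the patient a treatment failure.

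For UPCR, SAP 5.3.1.4 responds to a clinically significant increase or new start after baseline: "a sensitivity analysis will be performed where data is imputed after the point of ACE inhibitors/ARB treatment change". The rule is "The last observation prior to the start of concomitant medication will be carried forward to subsequent time points", with one limit: "Note that LOCF can only be applied within a treatment period and not across periods". The analysis is then carried "out similar to the primary and secondary analyses of UPCR as described in Sections 5.3.1.1 and 5.3.1.2". No multiple imputation, variance adjustment or reason for the choice is given.

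The model in SAP 5.3.1.1 is an MMRM on the log ratio to baseline. There, "In the MMRM model, missing data will not be imputed", and "Toeplitz covariance matrix will be used to model within-subject variance-covariance structure for the model errors". Section 5.3.1.1 does not remove values after an ACE inhibitor/ARB change. On timing, SAP 5.3 says: "Urinary protein:creatinine ratio (UPCR) is computed at Baseline, Weeks 1, 2, 4, 12, 20, 26 during the 26 week double-blind treatment period".

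For histology, SAP 5.2.1 and 5.2.3 use multiple imputation, with a missing-not-at-random sensitivity analysis.

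**The concern.** The analysis should answer a hypothetical question: what would the treatment difference in UPCR have been without the ACE inhibitor/ARB change? Carrying a value forward answers it by assuming that the patient's UPCR stops moving at the last visit before the change. That is a strong assumption for an outcome followed over 26 weeks of a treatment whose effect may take time to appear.

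Two consequences follow. If the effect is still building, patients who change keep only the part reached by then, so the contrast shrinks. If one arm changes more often and UPCR drifts in both arms, the arm with more frozen values is held back from the drift and a difference appears that treatment did not cause. A shift between the main analysis and this check could then come from the carry-forward rule rather than from ACE inhibitor/ARB use.

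**Working it through.** **1. The plan's own figure.** No figure is stated for UPCR. The only design calculation is for histology (SAP section 9): difference 35, SD 34, 90% power, two-sided alpha 0.05. The normal formula gives 2 × [(1.960 + 1.282) × 34/35]² = 19.8, so 20 per group. The t-based calculation needs 21 (90.2%), and 22 gives 91.5%. The planned 22 is reproduced; it is used below only as a sample size.

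**2. Attenuation with equal use.** Let f be the fraction changing in each arm and s the week of the carried value. The log effect is assumed to build linearly to Week 26. Both f and the time course are assumptions; Weeks 4, 12 and 20 are UPCR visits in the SAP.

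Share of the Week 26 log effect retained = 1 − f(1 − s/26)

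| f | s = 4 | s = 12 | s = 20 |
|---|---|---|---|
| 10% | 0.915 | 0.946 | 0.977 |
| 20% | 0.831 | 0.892 | 0.954 |
| 30% | 0.746 | 0.838 | 0.931 |

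For example, 1 − 0.3 × 22/26 = 0.746. The loss runs from about 2% to 25%. It depends on the time course: if the effect is complete by Week 12, values frozen at Week 12 or later lose nothing, and those frozen at Week 4 lose f × 8/12, or 7% to 20%.

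**3. Unequal use, no true effect.** If both arms drift to a ratio d by Week 26, with fractions f_P (placebo) and f_A (avacopan) changing:

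Apparent log ratio, avacopan to placebo = ln(d) × (f_P − f_A) × (1 − s/26)

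With f_P = 30% and f_A = 10%:
- d = 0.75, s = 4: −0.288 × 0.2 × 22/26 = −0.049, ratio 0.952. At s = 12 the ratio is 0.969.
- d = 1.25: 1.038 and 1.024. The direction reverses.

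**4. Simulation.** Assumptions: 22 per arm, six visits, residual log SD 0.5, Toeplitz covariance fitted by REML, change more likely after a high value, and about 19% of patients changing overall. There were 300 runs per scenario, with tests referred to t on 41 degrees of freedom. Entries are ratio; model SE/empirical SE; rejection rate.

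| Truth; changing placebo/avacopan | Carried forward | Set to missing, same model |
|---|---|---|
| 0.65; 20%/20%; no drift | 0.678; 0.154/0.161; 68% | 0.648; 0.161/0.168; 74.3% |
| 0.65; 30%/10%; no drift | 0.649; 0.153/0.157; 79% | 0.647; 0.162/0.165; 72% |
| No effect; 30%/10%; no drift | 0.977; 0.152/0.155; 5.0% | 0.995; 0.162/0.165; 4.7% |
| No effect; 30%/10%; fall to 0.75 | 0.945; 0.154/0.161; 7.7% | 0.995; 0.162/0.165; 4.7% |

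Row 1 matches step 2: ln 0.678 / ln 0.65 = 0.902 retained, against 0.892 for f = 20% and s = 12. In row 3, placebo patients are frozen more often at a high value, which alone gives 0.977. Row 4 adds the drift: 0.969 × 0.977 = 0.947, close to the simulated 0.945. In row 2 two errors cancel. Attenuation adds about 0.431 × 0.1 × 14/26 = 0.023 to the log ratio, and freezing at high values subtracts about 0.023 (ln 0.977). The Monte Carlo error of a 5% rejection rate is about 1.3 points, so 7.7% is roughly two such errors above nominal.

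**5. Standard error.** The carried-forward model SE is 4% to 6% below that of the alternative, but its empirical SE is lower too. Model SE divided by empirical SE runs from 0.957 to 0.981 when values are carried forward and from 0.958 to 0.982 when they are set to missing. The largest gap within a scenario (row 4, 0.957 against 0.982) is smaller than the Monte Carlo error of one empirical SE, about 1/√(2 × 299) = 4%.

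**The case against.** The strongest reply is that little depends on this section. It is one sensitivity analysis of a secondary endpoint. The gate-keeping in SAP 3.1 names only histologic activity and chronicity, so UPCR has no alpha-controlled test, and the main UPCR model does not impute. With equal use in both arms, carrying forward only dilutes the effect, so a positive result that survives it is informative. The alternative also rests on an untestable assumption, and the simulation made changes depend on observed UPCR, which favours a missing-at-random model. All of this stands. It limits the size of the point but does not remove the bias.

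Four stronger readings might be inferred and are not supported:
- **Copies treated as data understate the standard error.** Step 5 does not show this relative to the alternative.
- **The check cannot be interpreted.** This is too strong: under equal use the direction is known, and the bias was near zero in one scenario.
- **Nothing else addresses these changes.** This is the only defined UPCR analysis of starts and increases, but 5.3.1.4 allows further optional ones (its example is dose decreases), and SAP 4.4.1 summarises increased ACE inhibitor/ARB doses by arm.
- **Any RAAS change triggers the rule.** It applies to clinically significant ACE inhibitor/ARB increases or starts. The carried value is the last one before the change, which need not be early, and it stops at the period boundary.

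**Conclusion.** The point holds as a modest one. The carry-forward rule assumes a frozen UPCR. Under the assumptions in step 2 it removes about 2% to 25% of the Week 26 log effect. With unequal use and drift it produced spurious ratios of 0.952 to 1.038 in closed form, on either side of 1.

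These sizes are illustrations. The documents state no ACE inhibitor/ARB change rate, UPCR standard deviation or time course, and the number analysed may be below 22 per arm because 5.3.1.1 requires an abnormal baseline UPCR. The bias can be near zero, as in row 2, although there two errors happened to cancel. The main UPCR analysis and the primary endpoint do not depend on it.

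**What to change.** In SAP 5.3.1.4, set UPCR values after the ACE inhibitor/ARB start or increase to missing and refit the 5.3.1.1 MMRM. State that this estimates the treatment effect without the change, assuming missing at random. Keep the carried-forward version only as a supplementary display. Because a change may follow worsening that the model does not capture, a delta-adjusted variant can be added to test that assumption.

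Two details should be settled in the same edit. State how a Period A change affects Period B values and the Week 26 base: the present text bars carrying across periods, yet lists a comparison from baseline at Week 52. Also state how that comparison is handled. It is an ANCOVA without imputation, so a missing Week 52 value drops the patient unless a repeated-measures model is used.

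The cost is SAP wording and simple programming, with no new data. The downside is reliance on missing at random and a slightly wider interval: in the simulation the model SE rose from 0.152–0.154 to 0.161–0.162.

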8.3.2. Secondary and Other Endpoints

Secondary efficacy endpoints include:

1. The proportion of patients who have a histologic response, defined as a decrease (improvement) in the C3G Histologic Index for disease activity of at least 35% from baseline to Week 26 (see [Section 8.8](#) for basis of selection of 35% threshold);
2. The percent change from baseline in the C3G Histologic Index for disease chronicity over the placebo-controlled 26-week treatment period.

Other efficacy endpoints include:

1. The change and percent change from baseline in eGFR over the placebo-controlled 26-week treatment period;
2. The percent change from baseline in UPCR over the placebo-controlled 26-week treatment period;
3. The percent change from baseline in urinary MCP-1:creatinine ratio over the placebo-controlled 26-week treatment period;
4. Change from baseline in EQ-5D-5L (visual analogue scale and index) and SF-36 v2 (domains and component scores) over the placebo-controlled 26-week treatment period.

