2.3.2 Secondary Efficacy Endpoints

Secondary efficacy endpoints include:

- 1. The percent change from baseline in UPCR over the placebo-controlled 26-week treatment period;
- 2. The change and percent change from baseline in eGFR over the double-blind, placebocontrolled 26-week Treatment Period A;
- 3. The change from baseline in the C3G Histologic Index for disease chronicity over the placebo-controlled 26-week treatment period;
- 4. The proportion of subjects who have a histologic response, defined as a decrease (improvement) in the C3G Histologic Index for disease activity of at least 35% from baseline to Week 26 (see section 2.3.4).

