3.2.2 Intent-to-Treat Population

The Intent-to-Treat (ITT) Population will include all randomized subjects who received at least one dose of study medication; subjects with a histologic activity score of 0 at baseline or who are ongoing and have not completed the Week 26 visit will not be included in the ITT population.

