5.2 Primary Efficacy Analysis

The primary efficacy endpoint is the percent change from baseline to Week 26 in the C3G Histologic Index for disease activity. The C3G Histologic Index for disease activity can assume a score from 0-21. See Section 2.3.4 for further details on the calculation of C3G Histologic Index for disease activity.

Statistical Hypothesis Testing and Procedure

• The null hypothesis (H0) is that the avacopan group is not different from the placebo group when comparing the percent change from baseline to Week 26 in the C3G Histologic Index for disease activity.

• The alternative hypothesis (H1) is that the avacopan group is different from the placebo group when comparing the percent change from baseline to Week 26 in the C3G Histologic Index for disease activity.

Numbers, means, median, standard deviation, standard error of means, minimum and maximum will be presented by treatment group and study visit. Avacopan and placebo groups will be compared by Analysis of Covariance (ANCOVA) with treatment group as factor and baseline C3G Histologic Index for disease activity as a covariate. The LS mean estimate and corresponding 95% confidence interval (CI) will be estimated for the treatment main effect. The heterogeneity of the treatment effect across disease diagnoses and renal transplant strata may be investigated through subgroup analyses.

As there are no data available to access the possibility of non-normality distribution of percent change or change from baseline, normality distribution tests will be performed for both percent change and change from baseline. It is possible that the normality test would not hold for percent change from baseline or change from baseline or both. In this case, the following is the analysis procedures for the primary efficacy endpoint.

• If the test for normality fails for percent change from baseline at α level of 0.10 but not change from baseline, change from baseline will be used as the primary endpoint;

• If the test for normality fails for both percent change and change from baseline at α level of 0.10, percent change from baseline will be used as the primary endpoint, but non-parametric methodology will be used for the primary endpoint analysis. The van Elteren's test will be applied to test the percent change from baseline endpoint.

The treatment effect based on the baseline complement profile of subjects may also be investigated.

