5.2.1 Primary Analysis

The primary analysis will be based on the ITT population in the elevated C5b-9 stratum (>244 ng/ml). The primary analysis is based on percent change from baseline to Week 26 during the double-blind treatment period and will be analyzed using the ANCOVA analysis methods described above. Both percent change from baseline and change from baseline will be summarized and analyzed with percent change from baseline being the primary efficacy endpoint.

Multiple Imputation Method

Missing data used to calculate the primary endpoint will be handled using the Missing at Random (MAR) multiple imputation method. The multiple imputation procedure will be conducted in two parts using SAS[®] PROC MI and PROC MIANALYZE.

The primary analysis will be carried out by imputing missing data for the 7 lesions that comprise the Histological Index for Disease Activity. The multiple imputation model will include the two stratification factors (disease type [C3G or DDD] and kidney transplant status [Y/N]), treatment group, in addition to values at each visit from baseline through week 26. For each lesion component, 100 'complete' datasets will be generated using SAS[®] PROC MI. The seeds for the imputation will be specified as '12061', '36102', '94218', '20949', '60137', '80230' and '59137', for imputation of 7 lesion activity scores, respectively. Imputed individual lesion component scores will then be classified into scale scores (e.g., leukocyte infiltration % involvement = 29% would translate to a scale score of 2). The 'complete' datasets for the individual components of the lesion activity scores will be merged by imputation number and summed to calculate the Histological Index for Disease Activity and creation of 100 'complete' datasets for evaluation of activity scores.

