10 CHANGES FROM PROTOCOL-SPECIFIED STATISTICAL ANALYSES

- The protocol specified 3 analysis populations for the study including the primary elevated C5b-9 population, the non-elevated C5b-9 population and the combined population. Due to the small sample size in the non-elevated C5b-9 stratum, the primary elevated C5b-9 population will remain as the primary population and the two strata combined (including both elevated and non-elevated C5b-9) will be considered the secondary population for analysis. Data from the non-elevated C5b-9 stratum will only be summarized.
- ITT population definition change to exclude subjects who had baseline C3G Histologic Index of activity score of 0.
- Secondary efficacy endpoint order rearranged.

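### SAP 5.3.3 names absolute change in chronicity but sends the analysis to the percent-change rules of Section 5.2, which give no value at a baseline chronicity score of 0

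*SAP*

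**What the plan says.** **Endpoint definition.** Protocol 8.3.2 lists the secondary endpoint as "The percent change from baseline in the C3G Histologic Index for disease chronicity over the placebo-controlled 26-week treatment period". SAP 2.3.2 lists it as "The change from baseline in the C3G Histologic Index for disease chronicity over the placebo-controlled 26-week treatment period", and the heading of SAP 5.3.3 agrees: "Change from baseline in the C3G Histological Index for disease chronicity during the 26 Week placebo-controlled treatment period".

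**Testing status.** SAP 3.1 tests chronicity at 0.05 once the primary endpoint has succeeded in the same stratum. It is the only secondary endpoint given that status. SAP 3.1 does not name the scale.

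**Analysis rule.** The text of SAP 5.3.3 says "The analysis of C3G Histologic Index for disease chronicity will be carried as described in Section 5.2 for C3G Histologic Index for disease activity", and extends this to the secondary, completer and sensitivity analyses. In SAP 5.2.1 both scales are "summarized and analyzed with percent change from baseline being the primary efficacy endpoint". SAP 5.2 switches to absolute change if percent change fails normality and absolute change does not. If both fail, "percent change from baseline will be used as the primary endpoint, but non-parametric methodology will be used for the primary endpoint analysis". The code notes in Appendix 12.3 define CHG and PCHG for activity or chronicity and do not choose between them.

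**Zero scores.** SAP 3.2.2 removes from ITT "subjects with a histologic activity score of 0 at baseline". SAP 5.2.2 restricts the Week 26 to Week 52 percent change to patients whose Week 26 activity score is not 0. Neither rule mentions chronicity.

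**Disclosure.** On the secondary endpoints, SAP Section 10 says only "Secondary efficacy endpoint order rearranged".

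**The concern.** A formally tested endpoint needs one response variable, defined for every patient in the analysis set. Here the endpoint list names one scale, while the analysis paragraph imports a rule set that starts from the other and, in one branch, ends there. If a programmer follows 5.3.3 literally, the confirmatory chronicity test is run on percent change, and patients with a baseline chronicity of 0 have no response. They would leave the test without any stated exclusion, although they remain in ITT.

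The SAP authors dealt with the zero denominator for activity, at baseline and again at Week 26, so the gap for chronicity looks like an oversight rather than a decision. Percent change also weights the same histological step very differently by starting score, so the two scales can give different answers.

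**Working it through.** **1. The plan's own sample-size figure.** Protocol 8.8 and SAP 9 give 22 per arm per stratum for activity: difference 35, SD 34, 90% power, two-sided 0.05. The normal approximation gives n = 2(1.960 + 1.282)² × (34/35)² = 19.8, so 20 per arm. The exact t calculation needs 21 and gives 91.5% power at 22. The figure reproduces. The documents state no sample size or power for chronicity.

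**2. Can a baseline chronicity of 0 occur?** SAP 2.3.4 scores three lesions 0-3, with 0 meaning under 10% involvement, and one vascular item 0-1. The maximum is 3 × 3 + 1 = 10 and the minimum is 0, reached when all three lesions are under 10% and intimal thickening is less than the media. Protocol 4.3 sets only an upper limit on tubulointerstitial fibrosis (50%), and no criterion requires any chronicity. A total of 0 is therefore possible and eligible.

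**3. What percent change does on this scale.** A one-point worsening from baseline b is 100 × 1/b.

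| Baseline | 0 | 1 | 2 | 4 | 10 |
|---|---|---|---|---|---|
| One-point rise | undefined | +100% | +50% | +25% | +10% |

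Multiple imputation does not help. The Appendix 12.3 code fills missing Week 26 lesion values; an observed baseline of 0 is not missing and stays in the denominator. A record without a response contributes nothing to either the ANCOVA or the rank test.

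**4. The imported rule, branch by branch.**

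| Normality result | Variable under 5.2 | Baseline-0 patients |
|---|---|---|
| Percent change passes | percent change, ANCOVA | no value |
| Percent change fails, change passes | change, ANCOVA | included |
| Both fail | percent change, van Elteren | no value |

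Only the middle branch agrees with SAP 2.3.2. The trigger is also not unique: SAP 5.2 uses a normality level of 0.10, while Appendix 12.3 uses 0.01 for both indices.

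**5. Size of the loss.** The documents give no baseline chronicity distribution, so the share p with score 0 is an assumption. Patients lost = 44p; standard-error factor from the loss alone = 1/√(1 − p). The power column borrows the activity effect (35/34 SD) for chronicity, a second assumption, with 22(1 − p) per arm rounded.

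| p | Lost of 44 | SE factor | n per arm | Power |
|---|---|---|---|---|
| 0% | 0 | 1.00 | 22 | 91.5% |
| 5% | 2.2 | 1.03 | 21 | 90.2% |
| 10% | 4.4 | 1.05 | 20 | 88.7% |
| 20% | 8.8 | 1.12 | 18 | 85.1% |
| 30% | 13.2 | 1.20 | 15 | 77.7% |

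Even at 5%, the chance of at least one such patient among 44 is 1 − 0.95⁴⁴ = 89.5%.

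**6. Does the scale matter beyond the lost patients?** A simulation used 22 per arm, 4,000 runs, zero share 0-30%, other baselines uniform on 1-8, and change drawn as a rounded normal with SD 1.5. With an assumed 1.2-point effect, power was 66-71% for absolute change and 39-53% for percent change, and the two scales disagreed on significance in 23-32% of runs. These figures depend on the assumed distributions and show only that the choice is not neutral.

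**The case against.** The best defence is that the SAP does name the scale. SAP 2.3.2 distinguishes item by item: percent change for UPCR, both for eGFR, change for chronicity. The 5.3.3 heading agrees, and the SAP supersedes the protocol. On this view 5.3.3 borrows only the methods of Section 5.2 (ANCOVA, imputation, completer and sensitivity sets), and PCHG in Appendix 12.3 belongs to a shared code template. The appendix also speaks of the primary analysis of change from baseline for both indices.

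Much of this stands. A reader might infer that percent change will be the tested variable; the documents do not establish that. But 5.3.3 does not limit what it imports, and the 5.2 switch, which starts from percent change, has no clear meaning if only absolute change is in play. The appendix sentence does not settle it, because it uses the same word for activity, whose lead variable is percent change. Nor does the SAP's precedence over the protocol resolve an inconsistency inside the SAP.

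A reader might also infer that the scale could be picked after unblinding. The documents do not support this. The 5.2 switch is a written rule, and SAP Section 1 requires significant revisions of secondary analyses to be made before database lock or snapshot. In the simulation each scale alone rejected at about 5% under the null (4.5-5.4%). An inflated error rate would need a free choice of the better result, which no section allows.

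Finally, the documents show only that a score of 0 is permitted. They do not say it is common in early disease, or that scarring is easier to detect in those patients.

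**Conclusion.** The point holds as an unresolved and partly defective analysis rule for the one formally tested secondary endpoint. Followed literally, 5.3.3 can lead to a test on a scale other than the one named in SAP 2.3.2, and on that scale every patient with a baseline chronicity of 0 has no value. How many patients this affects cannot be known from the documents: about 2-13 of 44 for an assumed share of 5-30%, with a standard error 3-20% larger from the loss alone. At the low end the effect on power is small.

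Separately, the move from percent to absolute change is a departure from the protocol that Section 10 does not list.

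The reach is limited. The primary analysis, its sample size and the order of testing are untouched, and the chronicity test is run formally only if the primary endpoint succeeds in the same stratum. The point should be fixed, but it does not threaten the trial's main conclusion.

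**What to change.** In SAP 5.3.3, and consistently in 3.1 and Appendix 12.3:

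- Name absolute change to Week 26 in the chronicity index, by ANCOVA with baseline chronicity as covariate, as the sole formally tested chronicity variable. Say that patients with baseline 0 are included.
- State that the percent-change lead and the switch between scales in 5.2 do not apply to chronicity. If a rank-based fallback (van Elteren) is kept, apply it to absolute change and give one normality level, since 5.2 and 12.3 now differ.
- Report percent change in chronicity only descriptively, for baseline above 0. For Week 26 to Week 52, apply the same restriction to a Week 26 score above 0.
- Add the move from percent to absolute change to Section 10.

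The cost is SAP wording and a small edit to the analysis code, to be made before database lock. The downside is small: the tested scale will differ from the protocol's and from that of the activity endpoint, which the Section 10 entry should say openly.
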